5.4.3. Additional Safety Assessments

5.4.3.1. Clinical Laboratory Tests

5.4.3.1.1. Laboratory Test variables

Safety laboratory samples are centrally analyzed by ACM and the results are electronically transferred to sponsor's database. In exceptional cases, the protocol allows the utilization of local laboratories. Local laboratory analysis results are entered in the eCRF with some exceptions for blinding reasons (e.g., lymphocytes are not entered in the eCRF). Qualitative results like (marked) abnormality categorization, liver test elevation categories, etc., are derived from local laboratory data and summarized together with qualitative results derived from central laboratory data.

Safety laboratory assessments are conducted per schedule in section 6.12. Additional safety laboratory tests were allowed as per protocol at week 8, 16 and 20 and these assessments will also be tabulated.

Numerical results are converted into both conventional and SI units per QS document OTH-000005 (Definition of Marked Abnormalities in Laboratory Data). Results reported as below the lower limit of quantification (LLOQ) are set to the LLOQ value. Results reported as >XX are set to XX for calculation of summary statistics. For all quantitative safety laboratory data, core/extension baseline is flagged and absolute change from core/extension baseline and percent changes from core/extension baseline are calculated for each post-baseline value, as described in Section 5.1.6.

The Estimated Creatinine Clearance (eCLCr) is derived for analysis at each assessment (values based on Cockroft-Gault formula):

eCLCr (mL/min) = $(140 - \text{Age}) \times \text{baseline Weight (in kg)} \times \text{constant / serum creatinine (in } \mu\text{mol/L})$, where constant is 1.23 for men and 1.04 for women Or

eCLCr (mL/min) = $(140 - \text{Age}) \times \text{baseline Weight (in kg)} \times \text{constant / } (72 \times \text{serum creatinine (in mg/dL)})$ where constant is 1 for men, 0.85 for women

If the assessment comes from the core study (excluding the ones used as baseline value for the Extension Analysis Period):

- Age is re-calculated at each assessment as follows:
 Age at core screening (or re-screening) + 0.5 + (Date of laboratory assessment Date of core screening (or re-screening))/365.25.
- Baseline weight is the weight collected at core screening.

If the assessment comes from the core study but it is used as baseline for the Extension Analysis Period, or if the assessment comes from the extension study:

- Age is re-calculated at each assessment as follows:
 Age at start of extension + 0.5 + (Date of laboratory assessment Extension enrollment date)/365.25.
- Baseline weight is the weight collected at start of extension.

Flags are derived according to project specific ranges for marked laboratory abnormalities, as documented in Appendix 10. Marked laboratory abnormalities are labeled to indicate the increasing severity of abnormally low ("LL", "LLL"), or high values ("HH", and "HHH") for each of the laboratory parameters listed. For INR, the general range specified in the protocol is applied to all subjects irrespective of concomitant treatment with anticoagulants.

The following flags will be derived for Alanine aminotransferase (ALT), Aspartate aminotransferase (AST), Total bilirubin (TBIL), and Alkaline phosphatase (ALP) at the subject/assessment level:

- ALT: $\geq 1 \times ULN$, $\geq 3 \times ULN$, $\geq 5 \times ULN$, $\geq 8 \times ULN$, $\geq 10 \times ULN$, $\geq 20 \times ULN$
- AST: $\geq 1 \times ULN$, $\geq 3 \times ULN$, $\geq 5 \times ULN$, $\geq 8 \times ULN$, $\geq 10 \times ULN$, $\geq 20 \times ULN$
- ALT or AST: $\geq 3 \times \text{ULN}$, $\geq 5 \times \text{ULN}$, $\geq 8 \times \text{ULN}$, $\geq 10 \times \text{ULN}$, $\geq 20 \times \text{ULN}$
- TBIL $> 2 \times ULN$
- ALT or AST \geq 3 × ULN and TBIL \geq 2 × ULN (at the same sample date)
- ALT or AST \geq 3 × ULN and TBIL \geq 2 × ULN + AP < 2 × ULN (at the same sample date)
- INR value (ratio) > 1.5 combined with ALT or AST ≥ 3 ULN (at the same sample date).

In addition, the following treatment-emergent alerts regarding lymphocyte counts will be flagged:

- $< 0.2 \ 10^9/L;$
- $\geq 0.2 \times 10^{9}/L < 0.5 \times 10^{9}/L;$
- $\geq 0.5 \times 10^{9}/L < 0.8 \times 10^{9}/L;$
- $\geq 0.8 \times 10^{9}/L < 1.0 \times 10^{9}/L;$
- $> 1.0 \times 10^{9}$ L.

The following laboratory test will be presented in table and figure summaries. Other laboratory tests with abnormal findings will be presented in listings only.

Laboratory tests in standard unit
Erythrocytes (10^12/L)
Leukocytes (10^9/L)
Basophils (10^9/L)

Basophils/Leukocytes (%)
Eosinophils (10^9/L)
Eosinophils/Leukocytes (%)
Lymphocytes (10^9/L)
Lymphocytes/Leukocytes (%)
Monocytes (10^9/L)
Monocytes/Leukocytes (%)
Neutrophils (10^9/L)
Neutrophils/Leukocytes (%)
Platelets (10^9/L)
Hemoglobin (g/L)
Hematocrit (L/L)
Lactate Dehydrogenase (U/L)
Creatinine (umol/L)
Creatinine Clearance (mL/min)
Estimated Creatinine Clearance (mL/min)
Urea Nitrogen (mmol/L)
Urea (mmol/L)
Urate (umol/L)
Glucose (mmol/L)
Cholesterol (mmol/L)
Triglycerides (mmol/L)
Sodium (mmol/L)
Potassium (mmol/L)
Chloride (mmol/L)
Calcium (mmol/L)
Protein (g/L)
Albumin (g/L)
C Reactive Protein (mg/L)
Alanine Aminotransferase (U/L)
Aspartate Aminotransferase (U/L)
Alkaline Phosphatase (U/L)
Bilirubin (umol/L)
Prothrombin Intl. Normalized Ratio

5.4.3.1.2. Analysis of Laboratory Tests

The following tables will be produced for laboratory tests, both for the Combined Analysis Period, by core study treatment, using SAF (the summaries marked with § will include only the subjects who were initially treated with ponesimod 20 mg in the core study), and for the Extension Analysis Period, by core study treatment and overall, using the EXTS.

- Summary of absolute and absolute change from baseline values for laboratory tests (hematology, blood chemistry [excluding liver tests], liver tests): descriptive statistics by visit;
- Summary of percent change from baseline values for lymphocyte counts: descriptive statistics by visit;

CONFIDENTIAL – FOIA Exemptions Apply in U.S.

- Incidence of marked laboratory abnormalities (LL, LLL, HH, HHH) as defined in Section 6.10: frequency counts and percentages, where percentages are based on the number of subjects with at least one post-baseline value in the Analysis Period (i.e., number of subjects at risk);§
- Incidence of special laboratory abnormalities for ALT, AST, Bilirubin, and ALP: frequency counts and percentages, where percentages are based on the number of subjects with at least one post-baseline value (i.e., number of subjects at risk);§
- Incidence of marked treatment-emergent laboratory abnormalities for lymphocyte counts: frequency counts and percentages, where percentages are based on the number of subjects with at least one post-baseline value (i.e., number of subjects at risk)§.
- A plot to evaluate Drug-Induced Serious Hepatotoxicity (eDISH plot) based on the highest observed treatment-emergent ALT and total bilirubin values will be provided for safety analysis set during combined period, as well as for extension period by treatment group. Individual subject's values expressed as × ULN are plotted on a log-log scatter plot (ALT on the horizontal axis, total bilirubin on the vertical axis); reference lines are drawn at Hy's law thresholds, i.e., at 3 × ULN for ALT and at 2 × ULN for total bilirubin.

For abnormalities, the worst case in each direction is considered and summarized in all applicable categories, i.e., a subject counted in LLL is also counted in LL for a given parameter; also, a subject maybe counted in both the high and the low category for a given parameter.

[figure not shown]
Unscheduled assessments that meet the pre-defined high/low criteria will be flagged and may be included in the corresponding incidence tables.

In general, local laboratory results with missing visits labels are not included in any summary tables. However, due to regional crisis or other reasons, Central lab testing was not available for some patients and the laboratory tests were performed only locally. Therefore, data from local laboratory might also be considered for summary tables. Below is the hierarchy of assigning laboratory data for a definite nominal visit.

- 1. For nominal laboratory visit listed in section 6.12 (as well as the additional safety visit at week 8, week 16 and week 20), if there is scheduled central laboratory data, the results from the central laboratory data at this nominal visit will be used.
- 2. If there is no available scheduled central laboratory data at this nominal visit, data from centrally assessed unscheduled laboratory data attached to this nominal visit will be considered.
- 3. If there is no available central laboratory data attach to this nominal visit (neither scheduled nor unscheduled assessments), data from the following sources will be considered, within the time window of the nominal visit (see Table 7 for the visit window).
 - a. Locally assessed laboratory data within the designated visit window;
 - b. Remapped premature EOT at this designated visit window.

In case there are multiple data within the same visit window, the record closest to the scheduled target day will be selected for summary statistics. In case there are two records with equal distance to schedule target day, the one occurs after target day will be used.

Figure 2: Flowchart of selecting laboratory data for nominal visit

CONFIDENTIAL – FOIA Exemptions Apply in U.S.

In addition, the following figures will be produced for lymphocyte counts, both for the Combined Analysis Period, by core study treatment, using SAF, and for the Extension Analysis Period, using the EXTS:

• Summary of mean percent change from baseline values (and their standard error) for lymphocyte counts by visit: mean plot starting with zero change at baseline.

The specified abnormal findings (i.e. any laboratory test result of exceeding/not meeting the thresholds for marked laboratory abnormality in Section 6.10) in safety laboratory hematology, clinical chemistry and other laboratory parameters planned per protocol are also presented in subject data listings, for Extension Analysis Period only.

A listing will be created for all lymphocyte counts at each visit. The marked abnormality findings in lymphocyte count will be flagged in the listing.

For urinalysis no definitions and derivations necessary. Any resulting findings are recorded as adverse event (or medical history or relapse).

In addition, the following analysis will be performed for teriflunomide concentration which was measured at extension study day 1 for treatment group "Teriflunomide 14 mg / Ponesimod 20 mg".

- Number of subjects with teriflunomide concentration assessed.
- Number of subjects with non-detectable teriflunomide concentration
- Descriptive summary (N, arithmetic mean, SD, geometric mean, coefficient of variation [CV%], median, range, and IQ range) of the teriflunomide concentration in subjects whose sample were detectable.

A listing will be provided for all subjects with assessable teriflunomide concentration on extension study day 1.

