1.1.1. Safety objectives and endpoints

- To describe the long-term safety and tolerability of ponesimod 20 mg in subjects with Relapsing Multiple Sclerosis (RMS).
- To describe the effects of re-initiation of ponesimod treatment after interruption in subjects with RMS.

Table 2 details the endpoints that will be analyzed for the Extension Analysis Period and for the Combined Analysis Period. See Section 5.1.5 for further details regarding the analysis strategy for safety.

Table 2: Safety endpoints

Endpoints	Combined Analysis Period	Extension Analysis Period
Adverse events		
• Treatment-emergent AEs, SAEs, and AESIs #	Y*	Y
AEs leading to premature discontinuation of study treatment	Y	Y
Cardiac safety		
• Treatment-emergent morphological ECG abnormalities (as defined by the ECG provider)	Y*	Y
 Absolute values by visit for 12-lead ECG parameters (HR, PR, QRS, QT, QTcB, QTcF) 	Y	Y
 Change from baseline values by visit for ECG parameters (HR, PR, QRS, QT, QT QTcB, QTcF) 	Y	Y
• Change in ECG parameters (HR, PR, QRS, QT, QT QTcB, QTcF) from predose to selected post-dose assessments (1 h, 2 h, 3 h, 4 h) on day of re-initiation of study treatment	N	Y

Pulmonary safety

Table 2: Safety endpoints

Endpoints	Combined Analysis Period	Extension Analysis Period
• Absolute values and percent change from baseline in FEV ₁ and FVC at all assessments	Y	Y
• Treatment-emergent decrease from baseline > 20% and >30% in FEV ₁ or FVC	Y*	Y
• Treatment-emergent decrease from baseline > 20 percentage points in % of predicted FEV ₁ and FVC	Y*	Y
• Change in lung diffusion capacity as assessed by DL _{CO} (at selected sites only) expressed in absolute change (mL) and % of predicted value from baseline at all assessments	Y	Y
Other endpoints		
• Absolute values and change from baseline for HR, SBP, DBP, and body weight at all assessments	Y	Y
Treatment-emergent notable blood pressure abnormalities	Y*	Y
• Absolute values and change from baseline for laboratory tests (hematology, blood chemistry) at all assessments	Y	Y
Treatment-emergent notable laboratory abnormalities	Y*	Y

^{*} Cumulative safety data, e.g., AEs for the combined Analysis Period will only be presented for subjects who received 20 mg ponesimod in the core study.

Analyses on the Combined Analysis Period use the core baseline as a reference, while analyses on the Extension Analysis Period use the extension baseline as a refence.

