4.1.4. Safety set (SAF)

The safety set (SAF) includes all subjects who received at least one administration of core study treatment. Subjects will be analyzed according to the treatment they received during the core study.

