5.1.1.2. Combined Analysis Period

For efficacy, this period includes all available data from randomization in the core study up to extension EOS for subjects entering the extension, or until the core EOS date for subjects not entering the extension.

For safety, this period includes all available data from the date of first treatment administration in the core study up to the last treatment date in the extension study + 15 days for subjects entering the extension, or until the last treatment date in the core study + 15 days for subjects not entering the extension.

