5.1.2. Labels for treatment group

The following labels are used to indicate the subject's core / extension treatment allocations:

- Ponesimod 20 mg / Ponesimod 20 mg
- Teriflunomide 14 mg / Ponesimod 20 mg
- Total

If not otherwise specified, disposition demographic and efficacy analyses will be presented by treatment groups and total using labels "Ponesimod 20 mg / Ponesimod 20 mg", "Teriflunomide 14 mg / Ponesimod 20 mg" and "Total". Safety analyses will be presented by treatment groups and total using labels "Ponesimod 20 mg / Ponesimod 20 mg", "Teriflunomide 14 mg / Ponesimod 20 mg" and "Total", except the analyses for exposure, treatment-emergent event incidence and adverse events during combined period, that is only presented by "Ponesimod 20 mg / Ponesimod 20 mg" on SAF.

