5.1.6. Definition of treatment-emergent

A safety assessment (ECG, vital signs, laboratory, etc.) is considered treatment-emergent relative to the Analysis Period, and a safety event (AE, serious adverse event [SAE], Death, etc.) is considered treatment-emergent relative to the Analysis Period, if the assessment date is on or after the study treatment start date in the Analysis Period and prior to or on the study treatment end date + 15 days (inclusive). In case of planned pregnancy interruption, a safety assessment is considered treatment emergent relative to the Analysis Period if one of the following conditions is met:

- the assessment date is on or after the study treatment start date in the Analysis Period and prior to or on the last study drug intake date prior to pregnancy interruption + 15 days (inclusive)
- the assessment date is on or after the re-initiation date of study treatment after planned pregnancy and prior to or on the End of Treatment (EOT) date + 15 days (inclusive).

In case of multiple planned pregnancies interruptions, the above definition will be adapted, that any assessment in the following interval is not considered as treatment emergent: date between the last study drug intake date prior to each pregnancy interruption + 15 days (inclusive) and the reinitiation date of study treatment after each planned pregnancy (excluded).

If both the assessment date/time and the date/time of study treatment start (or of re initiation after planned pregnancy) are available, only events with date/time on or after the date/time of study treatment start (or of re initiation after planned pregnancy) are considered to be treatment emergent. In case of (partially) missing assessment dates/times, or for assessments on treatment Day 1 with reported assessment time contradicting the time point label, the nominal visit and time point labels will be used to determine whether an assessment is considered as treatment-emergent or not. For example, a blood pressure measurement with an assessment date on Day 1 but a missing assessment time or an assessment time after the time of first study drug intake, will not be considered treatment emergent if reported under the time point "Pre-dose" in the eCRF, however it will be considered treatment-emergent if reported as "2 hours post-dose" in the eCRF.

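### The combined-period eDISH plot lacks the § restriction carried by the neighbouring worst-case laboratory summaries, so a switcher's point can mix two drugs (minor)

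*SAP*

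**What the plan says.** SAP Section 5.4.3.1.2 lists laboratory outputs for both analysis periods and defines a mark for the combined period: "the summaries marked with § will include only the subjects who were initially treated with ponesimod 20 mg in the core study". The three incidence summaries carry that mark: marked abnormalities, the special ALT/AST/bilirubin/ALP abnormalities, and lymphocyte abnormalities. The next bullet is the eDISH plot, "based on the highest observed treatment-emergent ALT and total bilirubin values will be provided for safety analysis set during combined period". It has no §. The same bullet then asks for a second version of the plot, "as well as for extension period by treatment group".

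Three definitions decide what the unmarked bullet produces:

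- The safety set (Section 4.1.4) "includes all subjects who received at least one administration of core study treatment", so it contains the teriflunomide arm.
- For safety, the Combined Analysis Period (Section 5.1.1.2) covers "all available data from the date of first treatment administration in the core study up to the last treatment date in the extension study", plus 15 days, for subjects who entered the extension.
- An assessment is treatment-emergent (Section 5.1.6) if it falls "on or after the study treatment start date in the Analysis Period and prior to or on the study treatment end date", again plus 15 days.

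The general rule is in the Table 2 footnote (Section 1.1.1): cumulative safety data for the combined period "will only be presented for subjects who received 20 mg ponesimod in the core study". Table 2 applies this footnote to treatment-emergent notable laboratory abnormalities, among others. Sections 5.1.5.2 and 5.4.2.3 repeat the rule for cumulative data, giving AEs and SAEs as examples.

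**The concern.** An eDISH plot reduces each subject to one point: peak ALT against peak total bilirubin, read against the Hy's law thresholds of 3 × ULN and 2 × ULN. For a subject on one drug throughout, the point describes that drug. For a switcher in the combined period, the two peaks are taken over one window that spans teriflunomide, the gap between the studies, and ponesimod. One coordinate can come from each drug. A figure meant to evaluate drug-induced liver injury would then hold points that belong to no single drug, and the reader could not tell which ones.

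The other worst-case laboratory summaries in the same list avoid this through §. As the text stands, one programmer could follow the bullet and plot the whole safety set, while another could follow the general rule and plot core-ponesimod subjects only.

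**Working it through.** **1. Can a switcher's point mix drugs?** Section 5.1.6 counts from treatment start in the Analysis Period. For the combined period that is the first core dose, which is teriflunomide for a switcher. The only off-treatment time that Section 5.1.6 removes is planned-pregnancy interruption; the gap between the studies stays in. The bullet asks for the highest ALT and the highest bilirubin without a same-date or same-drug condition. Hypothetical example: core maxima of ALT 4 × ULN and bilirubin 0.8 × ULN, extension maxima of ALT 0.9 × ULN and bilirubin 2.5 × ULN. The combined point is (4, 2.5), inside the Hy's law quadrant, although neither phase alone gives a point there.

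**2. How do comparable outputs handle it?** Combined-period outputs in Sections 5.4.3.1.2 to 5.4.3.4.2 that report a worst case or any occurrence:

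| Domain | Outputs | Limited to core ponesimod |
|---|---|---|
| Laboratory incidence | 3 | 3 |
| eDISH | 1 | 0 |
| Blood pressure | 1 | 1 |
| ECG | 2 | 2 |
| Spirometry | 1 | 1 |
| DLco | 1 | 1 |
| Total | 9 | 8 |

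Outside these sections the restriction is also absent from MACE (5.4.2.3.6), eC-SSRS (5.4.3.9.2) and the combined-period lymphocyte incidence line in 5.5.3. The last repeats an output that carries § in 5.4.3.1.2. None of these three joins two separate maxima in one point.

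**3. How many points could be misplaced?** The SAP gives no figure to reproduce, so this is a sizing under assumptions.

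From the SAP: 1133 randomized and 877 enrolled in the extension (Section 3); 108 core weeks and up to 240 extension weeks (Section 1.2).

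Assumed: 40% to 60% of the 877 are switchers (351 to 526; 438.5 at an even split); 3% to 10% ever reach ALT ≥ 3 × ULN (p); 1% to 2% ever reach bilirubin ≥ 2 × ULN (q); events are independent, with constant rates over treatment time.

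Teriflunomide share of a switcher's treatment time, s: 108/(108+240) = 0.310 if treated to extension Week 240; 108/(108+48) = 0.692 if treated to Week 48; 0.5 is the worst case.

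Phase probabilities:

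- a1 = 1−(1−p)^s and a2 = 1−(1−p)^(1−s) for ALT
- b1 = 1−(1−q)^s and b2 = 1−(1−q)^(1−s) for bilirubin

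Probability of being in the quadrant overall but in neither phase alone:

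P = a1(1−a2)·b2(1−b1) + a2(1−a1)·b1(1−b2)

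Worked case with s = 0.310, p = 0.10, q = 0.02: a1 = 0.03217, a2 = 0.07009, b1 = 0.00625, b2 = 0.01384. P = 0.000829, and 438.5 × 0.000829 = 0.364 subjects.

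Expected subjects at an even split:

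| | s = 0.310 | s = 0.692 | s = 0.5 |
|---|---|---|---|
| p = 0.03, q = 0.01 | 0.056 | 0.055 | 0.065 |
| p = 0.10, q = 0.02 | 0.364 | 0.362 | 0.425 |

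Over the 40% to 60% range the minimum is 0.044 (n = 350.8) and the maximum 0.510 (n = 526.2, s = 0.5). The expected count stays below one.

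**4. What does the restriction remove?** Subjects who did not enter the extension: 1133 − 877 = 256. The teriflunomide share is 128 at one half (102 at 40%, 154 at 60%). This count starts from randomized rather than treated subjects, so it is approximate.

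**The case against.** The strongest reply is that the general rules already restrict the plot. A display of each subject's highest treatment-emergent values is cumulative data, and the Table 2 footnote limits such data to core-ponesimod subjects. That may well be what was meant. But none of the general rules names the eDISH plot, and the presentation rule in Section 5.1.2 shows both arms "except the analyses for exposure, treatment-emergent event incidence and adverse events during combined period", a list that does not plainly include a scatter plot of maxima. If the reply is right, the bullet is missing its mark, and adding § is still the correction.

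A second reply is that a missing mark proves little in this SAP, since the lymphocyte line in Section 5.5.3 omits the restriction that Section 5.4.3.1.2 gives. This stands as far as intent goes: the absence of § does not show that the sponsor chose to include switchers. Nor does the reference to the safety set, because the §-marked outputs are also on that set.

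A third reply is that outputs are given by core study treatment, so switchers would probably form their own labelled group. That helps the reader but does not separate the two drugs within one point.

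Two stronger readings are tempting. A reader might infer that the plan loses sight of ponesimod's liver effect in switchers. It does not: the extension-period plot shows them on ponesimod, and Section 5.4.3.1.1 flags ALT or AST together with bilirubin on the same sample date. A reader might also infer that pairing peaks from different dates is itself wrong. The documents give no ground for that, and core-ponesimod points do the same within one drug.

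**Conclusion.** The point holds as a minor error in the text. As written, the combined-period eDISH plot departs from the SAP's own rule for cumulative combined-period safety data, and it allows a switcher's point to combine two drugs. Only switchers' points in this one figure are affected. Core-ponesimod points, teriflunomide points from subjects who stayed out of the extension, and the extension-period plot are sound.

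The expected number of spurious Hy's law points is 0.04 to 0.51. This rests on assumed event rates, an assumed switcher share, and independent, constant hazards; none of these comes from the SAP. It counts only threshold crossings: any switcher whose two peaks fall in different phases has a mixed point wherever it lies. The study is descriptive and tests no hypotheses (Section 2), so no formal conclusion depends on this. Priority is low. It would be too strong to call eDISH the only unrestricted cumulative output in the SAP, given MACE, eC-SSRS and the lymphocyte line in Section 5.5.3.

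**What to change.** Add § to the combined-period part of the eDISH bullet in Section 5.4.3.1.2, so that this plot shows core-ponesimod subjects only. Leave the extension-period plot by treatment group as it is. The cost is one symbol in the SAP and one data filter in the figure program. The downside is that valid points from teriflunomide subjects who never entered the extension, about 128 if the arms are even, leave the combined figure.

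An alternative keeps both arms and takes teriflunomide-arm maxima from core data only, up to core EOT + 15 days and cut at the first ponesimod dose. The cut is needed because FU1 can fall 14 days after the last core dose (Section 1.2.1). This retains those points, but it puts different periods for the two arms into one figure labelled as combined, so the § is the simpler correction.
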